0.3 Received wrong treatment or was overdosed (only after unblinding)

A subject is considered to have received wrong treatment if they were randomized to study drug **A** but instead received study drug **B** at some point during the study. Any subjects who received wrong treatment on 1 or more days during the double-blind treatment period will be considered IPDs. These subjects will be identified programmatically after study data unblinding.

The drug dispensing record based on the Study Drug Administration / Drug Accountability CRF page will be presented in a data listing. The number of tablets taken from each blister card will be calculated, as well as the number of tablets should have been taken from the card. If for a given card the number taken is larger than the number should have been taken, that card will be flagged for study drug overdose. Additional 'study drug overdose' incidences may be identified from the protocol deviations log and/or investigator comments.

The IPD review team will determine if any of the incidences identified above constitutes a potential IPD. These determinations are made without knowledge of which treatment (placebo or SEP-4199) the subject was actually overdosed with.

After unblinding, those incidences that were determined to be a potential IPD with the treatment involved being SEP-4199 will be considered IPDs.

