5. ANALYSIS POPULATIONS

Agreement and authorization of subjects included/ excluded from each analysis population will be conducted prior to the unblinding of the study.

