5.2. PER PROTOCOL [PP] POPULATION

The per protocol (PP) population will consist of all ITT subjects who have no important protocol deviations (IPD), as determined during the IPD review meetings, that may affect the interpretation of the primary efficacy endpoint as defined in [Section 2.6.1](#). See [APPENDIX 7](#) for specifications of IPD. New IPD categories may be created through the review of investigator comments and/or protocol deviations log. The predefined and any new IPDs are defined during the Blinded Data Review (BDR) Process. See [APPENDIX 6](#) for specifications of the BDR Process. Subjects in the PP population will be analyzed according to their randomized treatment group.

Analysis of the primary and the secondary efficacy endpoints will also be performed using the PP population and analyzed according to the randomized treatment group.

Document:

Author:

Version Number:
Version Date:

V2.0

21MAY2020

Template No: CS_TP_BS016 Revision 4
Effective Date: 01Apr2016

Reference: CS_WI_BS005

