It should be noted that the identification of IPDs related to receiving wrong treatment requires unblinded data. Therefore, no data listing will be provided during the IPD review; these IPDs will be identified programmatically using the approved criteria after database hard lock and treatment unblinding. Similarly, only potential IPDs related to study drug overdose will be identified during the IPD review. IPDs related to SEP-4199 overdose can only be ascertained after treatment unblinding.

The approved manual IPD determinations and programmable IPD criteria will be provided to the IQVIA Biostatistics team. Programmable IPDs will be identified based on the final, unblinded study data using the approved programming criteria. Both programmable and manually determined IPDs will be included in the analysis dataset and used in downstream derivations.

The entire IPD review process will be completed prior to database hard lock.

Document:

Author:

Version Number:

V2.0

Version Date:

21MAY2020

Template No: CS_TP_BS016 Revision 4
Effective Date: 01Apr2016

Reference: CS_WI_BS005

IPD SPECIFICATIONS

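### A blinded overdose finding becomes an important protocol deviation only if the drug was SEP-4199, so the supportive per-protocol set can exclude active subjects and keep placebo subjects with the same tablet counts

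*SAP*

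**What the plan says.** SAP Appendix 7, item 0.3 handles overdose in two stages.

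- **Blinded stage, all arms.** Tablet counts are checked card by card: "If for a given card the number taken is larger than the number should have been taken, that card will be flagged". The review team then decides which incidents are potential important protocol deviations (IPDs). The SAP adds: "These determinations are made without knowledge of which treatment (placebo or SEP-4199) the subject was actually overdosed with".
- **Stage after unblinding.** Of those potential incidents, only the ones "with the treatment involved being SEP-4199 will be considered IPDs". The review-process part of Appendix 7 says the same: "IPDs related to SEP-4199 overdose can only be ascertained after treatment unblinding".

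IPDs determine the per-protocol (PP) set. SAP Section 5.2 says it "will consist of all ITT subjects who have no important protocol deviations (IPD), as determined during the IPD review meetings", limited to deviations that may affect interpretation of the primary endpoint. Appendix 7 adds: "Both programmable and manually determined IPDs will be included in the analysis dataset and used in downstream derivations". The PP set is used to repeat the primary and secondary analyses (SAP Sections 16.1.5.2 and 16.2.5). Section 7.4 presents the primary repeat as information on robustness.

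On timing, Section 5 says that agreement on "subjects included/ excluded from each analysis population will be conducted prior to the unblinding of the study". Appendix 7 says: "The entire IPD review process will be completed prior to database hard lock".

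Item 0.4 is a separate rule that applies in every arm: overall compliance below 75% or above 125% is an IPD. Protocol Section 15.3.3 lists the same compliance rule and no overdose rule specific to SEP-4199, although its list is not exhaustive.

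**The concern.** The blinded stage treats the arms alike; the final step does not. Two subjects may take the same number of extra tablets and receive the same blinded judgement, yet the actual treatment alone decides whether that judgement becomes an IPD. Irregular tablet-taking marks adherence behaviour in any arm, and it may be related to outcome. Filtering it more strictly in the active arms can therefore shift the PP contrast for reasons unrelated to the drug.

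At stake is how far the PP repeat can be read as a robustness check on MADRS and CGI-BP-S. A secondary issue is timing: a PP list that depends on a treatment look-up cannot be fully agreed before unblinding, as Section 5 requires.

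**Working it through.** The plan states no overdose rate and no expected PP exclusions, so it has no figure of its own to reproduce. Three checks follow.

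**1. The same blinded judgement in each arm**

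| Step | SEP-4199 subject | Placebo subject |
|---|---|---|
| Card shows more tablets taken than due | flagged | flagged |
| Team judges it a potential IPD, blind | yes | yes |
| Look-up after unblinding (0.3) | IPD | not an IPD |
| May affect interpretation of the primary endpoint (5.2) | if yes, out of PP | not reached; stays in PP unless another IPD applies |

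**2. Does item 0.4 catch the placebo subject instead?**

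Inputs: 18 tablets per card (Protocol 9.2.1); one or two cards per visit (Protocol 9.4); two tablets per day, with overall compliance = tablets taken ÷ (2 × days of exposure) (SAP 14.1 and 15.1). Six cards in total is an inference: dispensing on Days -1, 7, 14 and 28 for intervals of about 7, 7, 14 and 14 days gives 1 + 1 + 2 + 2 = 6. Tablets dispensed = 6 × 18 = 108.

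| Days of exposure | Tablets due | Highest possible compliance | Fewest tablets for > 125% | Extra tablets |
|---|---|---|---|---|
| 40 | 80 | 108/80 = 135.0% | 101 | 21 |
| 42 | 84 | 108/84 = 128.6% | 106 | 22 |
| 43 | 86 | 108/86 = 125.6% | 108 | 22 |
| 44 | 88 | 108/88 = 122.7% | 111, not reachable | – |

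At 42 days, 1.25 × 84 = 105, so 106 tablets are needed, or 22 of the 24 spares. A placebo completer who takes up to 21 extra tablets is not an IPD under the upper limit. A SEP-4199 subject can become an IPD through a single card that the team judges important.

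The upper limit is easier to reach for early discontinuers. With 5 days of exposure, 10 tablets are due and 1.25 × 10 = 12.5, so 13 tablets (3 extra) suffice. The lower limit of 75% applies to placebo in full.

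**3. How far could the PP contrast move?**

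Let f be the share of an active arm removed by the overdose rule. Let s be the gap in mean MADRS change between those subjects and the rest of the arm. Removing them shifts that arm's mean by −f × s; placebo has no matching shift under this rule. Both inputs are assumptions.

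| f | Of 98 planned per arm | s (points) | Size of shift | Share of planned 3.85 |
|---|---|---|---|---|
| 2% | 2.0 | 2 | 0.04 | 1.0% |
| 5% | 4.9 | 5 | 0.25 | 6.5% |
| 10% | 9.8 | 8 | 0.80 | 20.8% |

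If flagged subjects do worse than the rest, the shift favours SEP-4199; if they do better, it favours placebo. If the rule applied to all arms with equal f and s, the terms would cancel.

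**The case against.** The strongest defence is that extra placebo tablets deliver no active drug, so only an active overdose could affect the endpoint in the sense of Section 5.2. That reading is arguable, but the SAP does not state it. It supports a separate safety table more than it supports choosing an efficacy set by actual treatment, because irregular tablet-taking is an adherence marker in every arm.

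Some stronger readings are tempting, and the documents do not support them:

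- **Irregular tablet-takers leave the active arms only.** Not so. Item 0.4 makes placebo subjects below 75% or above 125% IPDs as well.
- **Every flagged SEP-4199 subject is removed.** A flag is not enough. The team must judge the incident important while blind, and the deviation must be one that may affect interpretation of the primary endpoint.
- **The PP set is chosen with knowledge of treatment.** The judgement is made blind. What follows is a pre-specified, mechanical look-up with no discretion.
- **Appendix 7 contradicts itself on timing.** It can be read consistently: the review ends before hard lock and the look-up follows. The conflict with Section 5 is harder to remove, because the list of excluded subjects is not final until treatment is known.
- **The overdose rule is the sole cause of that conflict.** Wrong-treatment IPDs also need the treatment code, although they apply to all arms. Removing the overdose filter does not settle the timing by itself.
- **The randomized comparison is otherwise intact in the PP set.** PP already conditions on behaviour after randomization, such as compliance and concomitant medication. This rule adds a difference between arms to that.

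The PP analysis is also not the only robustness check. The placebo-based imputation, tipping-point and ANCOVA analyses all use the ITT population.

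**Conclusion.** The point holds in a limited form. Item 0.3 makes the overdose IPD depend on treatment arm, so identical tablet counts and identical blinded judgements can exclude a SEP-4199 subject from PP and keep a placebo subject. Item 0.4 softens this but does not cure it: assuming six cards, its upper limit needs at least 106 of 108 tablets over 42 days and cannot be reached at 44 days.

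The effect is confined to the supportive PP analyses of the primary and secondary endpoints. The ITT population is primary for all efficacy analyses (SAP 5.1), and PP lies outside the Hochberg procedure (SAP 7.4), so the primary result, its power and its type I error do not change. The illustrative range of 0.04 to 0.80 MADRS points rests wholly on assumed inputs. The actual size and direction are unknown. This is a modest flaw, worth correcting because the correction is nearly free.

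**What to change.** 1. In Appendix 7, item 0.3, delete the sentence that limits overdose IPDs to SEP-4199, and delete the matching sentence in the review-process part. State instead that an overdose incident judged important by the review team is an IPD in any arm, and that this determination is final before unblinding.
2. Tabulate overdose with active drug separately, as a safety summary.
3. Reconcile Section 5 and the closing sentence of the Appendix 7 review process with item 0.3. Say that wrong-treatment IPDs, which apply to all arms, are the only ones identified after unblinding, and that their criteria are fixed beforehand. Limit the after-unblinding note in the heading of 0.3 to wrong treatment.

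The cost is SAP wording, and a few more placebo subjects may leave the PP set. No data collection, sample size or primary analysis changes.

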0.4 Overall double-blind compliance rate < 75% or > 125%

The overall compliance rate of the double-blind treatment period is calculated as: (number of tablets taken / number of tablets should have been taken) × 100%. Subjects whose overall compliance rate is < 75% or > 125% will be identified programmatically. These subjects will be considered IPDs. Subjects whose overall compliance rate cannot be calculated will not be considered IPDs.

0.5 Received benzodiazepines, sedatives or hypnotics within 8 hours of a subsequent efficacy assessment

Protocol section 10.3.3 specifies: "Benzodiazepines, sedatives or hypnotics should not be administered within 8 hours prior to any psychiatric assessments."

For a given study visit, the date and time of the last dose of benzodiazepines, sedatives or hypnotics taken immediately before the visit, and the collection start date and time of efficacy assessments at the visit, will be used to identify subjects who took any benzodiazepines, sedatives or hypnotics medications within 8 hours of a subsequent efficacy assessment. Such cases will be identified programmatically and flagged in a data listing. The IPD review team will determine whether any of these cases constitutes an IPD.

0.6 Treatment unblinded during double-blind period

Subjects whose treatment was unblinded during the double-blind period and who completed additional assessments on MADRS or CGI-BP-S after unblinding will be considered IPDs.

Subjects whose treatment was unblinded will be identified based on the Subject Disposition – End of Study CRF page and presented in a data listing. The date of unblinding will be based on the IRT data transfer. Those subjects who have MADRS or CGI-BP-S data collected on or after the date of unblinding will be identified programmatically and flagged in the listing. The complete MADRS and CGI-

Document:

Author:

Version Number:

V2.0

Version Date:

21MAY2020

Template No: CS_TP_BS016 Revision 4
Effective Date: 01Apr2016

Reference: CS_WI_BS005

S assessment records for all unblinded subjects will be provided in a separate listing.

0.7 Tested positive for urine drug screen

All urine drug screen results will be presented in a data listing. The IPD review team will determine for each positive result whether this constitutes an IPD.

0.8 Missing laboratory results before randomization

All subjects with a complete missing laboratory category evaluation (either Chemistry, Hematology, or Toxicology) will be presented in a data listing. The IPD review team will determine for each missing assessment before randomization whether this constitutes an IPD.

Document:

Author:

Version Number:

V2.0

Version Date:

21MAY2020

Template No: CS_TP_BS016 Revision 4
Effective Date: 01Apr2016

Reference: CS_WI_BS005

APPENDIX 8. EQ-5D-5L INDEX VALUE

EQ-5D-5L health states, defined by the EQ-5D-5L descriptive system, will be converted into a single index value using an appropriate value set. For international trials, EuroQol recommends applying a single value set or crosswalk to all study sites. US value set will be used for US, Europe, and Japan for this study. Please refer the following EuroQol website for EQ-5D-5L value sets and further information.

<https://euroqol.org/publications/key-euroqol-references/value-sets/>

Document:

Author:

Version Number:

V2.0

Version Date:

21MAY2020

Template No: CS_TP_BS016 Revision 4
Effective Date: 01Apr2016

Reference: CS_WI_BS005

Document Approval Signature(s)

This document has been signed electronically in compliance with IQVIA and IQVIA Companies' electronic signature policies and procedures. This page is a manifestation of the electronic signatures, which may be confirmed within the IQVIA and IQVIA Companies' source system in accordance with IQVIA and IQVIA Companies' records retention policies.

Note: the Title field in the signature block has been intentionally left blank.

UserName: [name] (q1010574)

Title:

Date: Friday, 22 May 2020, 03:29 AM Eastern Time

Meaning: I Approve the Document

=====
